10.4. DESCRIPTION OF STATISTICAL METHODS

10.4.1. GENERAL APPROACH

This is a prospective, single arm, open label, controlled study to evaluate the impact of Spirox Latera™ alone or in conjunction with other procedures over 24 months of follow-up. Each subject will serve as their own control, and changes from baseline are of primary interest.

The study reference day (Day 1) is the day of Visit 3 (Treatment).

“Baseline” NOSE score refers to the measurement taken prior to the start of the procedure during the baseline visit.

Continuous variables will be summarized with descriptive statistics (N, mean, SD, median, quartiles), and categorical variables will be summarized as N (%).

Unless otherwise indicated, all p-values and confidence intervals will be 2-sided.

10.4.2. ANALYSIS OF THE PRIMARY EFFICACY ENDPOINT(S)

The primary endpoint will be the proportion of treatment responders at 6 months post procedure. The mITT analysis dataset will be used to analyze the primary endpoint.

Responder is defined as a subject that has at least one (1) NOSE class improvement or at least 20% NOSE score reduction compared to baseline.

Subjects will be classified as non-responders if neither of these criteria is met.

NOSE score is a PRO instrument which measures the impact of nasal obstruction on quality of life. It is scored in increments of 5 points, and the total score is calculated as the sum of all 5 questions multiplied by 5, where the range is 0 (asymptomatic) to 100 (most extreme deleterious impact on quality of life). The NOSE score classes¹⁷ are based on the total calculated score:

- Mild:** 5 – 25 points
- Moderate:** 30 – 50 points
- Severe:** 55 – 75 points
- Extreme:** 80 – 100 points

This primary hypothesis will be evaluated for the mITT using a -2-sided exact test²³, and the corresponding exact (Clopper-Pearson) 2-sided 95% confidence interval will be calculated. The null hypothesis that the proportion of responders is $\neq 0.5$ will be rejected if the p-value is < 0.05 .

Sensitivity analyses will be conducted to determine the impact of missing data on these results. These analyses will depend on the extent of missing data, and will be detailed in the SAP, but may include:

1. Last observation carried forward (LOCF)
2. Subjects with missing data classified as non-responders
3. Re-implanted subjects classified as non-responders

This analysis will be repeated for the Latera stand-alone Population alone. While this study is not sufficiently powered to reject the null hypothesis for this subgroup, the response rate, 95% confidence interval and p-value will be calculated. See section 10.5 for further details.

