2.2. PRIOR INVESTIGATIONS

A prior study of this device was performed in the setting of an EC approved protocol in Germany. The study was conducted at three institutions under the oversight of Co-Principal Investigators, [name], MD and [name] in Munchen, Germany. This prior first in man investigation evaluated the safety and performance of the Spirox device and its ability to support upper and lower lateral cartilage in subjects with nasal valve collapse as primary contributor to nasal airway obstruction (NAO) under general or local anesthesia. A brief summary of this prior investigation follows.

Fourteen (14) cases were performed in an operating suite under general anesthesia and sixteen (16) cases were performed in a clinic-based setting under local anesthesia. A total of fifty-six Implants were placed in thirty subjects. Subjects with a Nasal Obstruction Symptom Evaluation (NOSE) scale score ≥ 55 and Nasal Valve Collapse as primary contributor to NAO were eligible. Follow-up visits occurred at week 1 and months 1, 3, 6, 12 and 18 post procedure. These visits included documentation of medical history, physical exam, NOSE score and digital photography. The NOSE scale is a validated as a Quality of Life (QOL) instrument¹⁸. It uses a 20-point scale to capture severity of breathing symptoms, with higher scores indicating more severe symptoms than lower scores. The results are converted to 100-point scale by multiplying the total score by five.

There was a total of five (5) device-related adverse events reported in four (4) subjects. These events included 1 case of hematoma, 1 case of inflammation, and 3 Implant retrievals. All events resolved with no clinical sequelae. Investigators concluded that the 3 Implant retrievals were the result of suboptimal implantation methods or possible significant patient lateral wall manipulation during the first post-operative week and were not caused by adverse physiologic tissue rejection or infection. The Implant placement procedure was revised during the course of the study to address suboptimal implantation techniques and no further retrieval events occurred.

To date, all follow up visits through 18 months have been completed; 15 out of 30 subjects completed 18 months of follow up. Three subjects have had other nasal surgery procedures and consequently exited the study; two subjects after the 12 month visit and one subject after the 18 month visit.

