7.6. PROHIBITED MEDICATIONS, TREATMENTS, AND PROCEDURES

Concomitant medications or therapies preventing subjects from being eligible to participate in this study are current use of nasal oxygen, CPAP, chronic use of systemic steroids and/or recreational intra-nasal drugs. Additionally, concomitant radiation exposure in the treatment area or chemotherapy will deem a subject ineligible to participate.

In addition, the following treatments will not be permitted concurrent with index procedure or within 24 months after index procedure:

- Functional Endoscopic Sinus Surgery (FESS)
- Sinuplasty procedure
- Rhinoplasty procedure
- Any surgical or non-surgical treatment of the nasal valve, other than the index procedure, within 12 months of the study
- Use of a dilator and/or an external device in the nasal area (e.g. nasal strips).

SPACE LEFT INTENTIONALLY BLANK

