7.8. EARLY TERMINATION VISIT

In the event of an early subject termination, the clinical site should, at a minimum, document Adverse Events and Concomitant Medications changes. Refer to **Section 7.7** Schedule of Events.

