10. STATISTICAL CONSIDERATIONS

10.1. STATISTICAL AND ANALYTICAL PLANS

A Statistical Analysis Plan (SAP) will be finalized prior to database lock, which will contain further analysis details and statistical methods.

All efficacy endpoints will be analyzed using data collected after the training cases are completed. The training cases will not be included in the efficacy endpoint analyses. The training cases will be summarized with descriptive statistics for information purposes only and will include a summary of adverse events.

The subjects that receive a replacement implant will be included in the modified Intention-to-Treat population but excluded from the per-protocol population. A separate sensitivity analysis will be conducted in which the subjects that received a replacement implant are considered non-responders.

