10.4.3. ANALYSIS OF THE SECONDARY ENDPOINT(S)

Response proportion as defined in section 10.4.2 will be evaluated for the 1, 3, 12, 18 and 24 month follow-up visits using the same technique as described for the primary endpoint.

Change in nasal airway obstruction from baseline at 1, 3, 6, 12, 18 and 24 months post-procedure as reported by subjects on a VAS 0-100 mm scale (0= no difficulty breathing through nose; 100mm=not-able to breathe through nose) will be analyzed using a mixed model for repeated measures (MMRM). Least-square mean change from baseline and corresponding 95% confidence intervals will be reported.

Baseline VAS score will be analyzed in a separate model, including decongestant use as a covariate. Decongestant use will be considered at baseline only to visualize the turbinate contribution to overall obstruction, thus no decongestant VAS will be assessed at the follow-up visits.

Results from the subject satisfaction questionnaire will be tabulated at 6 months. Sensitivity analyses for missing data will be described in the SAP.

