10.5. SAMPLE SIZE

The primary study hypothesis is a superiority comparison to a target proportion:

Null Hypothesis H_0 : the proportion of responders at 6 months is =0.50, versus
Alternative Hypothesis H_A : the proportion of responders at 6 months is $\neq 0.50$

See section 10.4.2 for the definition of response. This hypothesis will be evaluated using an exact test.

In order to have $> 90\%$ power to rule out a response rate $\leq 50\%$ at a 5% (2-sided) significance level, assuming a true response rate of 66%, 150 subjects with 6 month follow-up are needed. Assuming about 10% drop-out rate, up to 170 subjects will be enrolled. All mITT subjects will be used for this comparison, regardless of protocol deviations.

The assumed response rate is the minimum value is expected to be consistent with previous trials, where an 80% response rate at 6 months was observed.

The anticipated size of the Latera stand-alone Population is 50 subjects. With only 50 subjects in this cohort, the power to reject the primary null hypothesis is approximately 63%, given a true response rate of 66%. Although this cohort is not sufficiently powered to show significance for a true response rate of 66%, the p-value and exact binomial 95% confidence interval will be calculated for this population. Retrospective power for the actual response rate will also be calculated for this comparison in order to contextualize the results.

Sample size calculations were performed using the package RCT Design for R version 3.2.3.

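### The 18- and 24-month responder rates have no scoring rule for other nasal surgery; at the prior study's 3 of 30, exits alone would raise the 24-month rate by about 7 to 8 points

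*Combined protocol and SAP*

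**What the plan says.** **Response rule.** Section 10.4.2 counts a subject as a responder on an improvement of at least one NOSE class or a NOSE reduction of at least 20% from baseline. It then says: "Subjects will be classified as non-responders if neither of these criteria is met". Section 10.4.3 evaluates the later visits, including 18 and 24 months, "using the same technique as described for the primary endpoint".

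**Other procedures.** Section 7.6 says that "the following treatments will not be permitted concurrent with index procedure or within 24 months after index procedure", and lists sinus surgery, sinuplasty, rhinoplasty, other nasal valve treatment and dilators. It gives no rule for scoring a subject who has one of them.

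**Who is analysed.** Section 10.5 states: "All mITT subjects will be used for this comparison, regardless of protocol deviations". It also says that "150 subjects with 6 month follow-up are needed". In section 10.4.2, treating missing data as non-response is only one of the sensitivity analyses that may be run. The per-protocol set in section 10.3 removes subjects without a 6-month score and re-implanted subjects, and no one else.

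**Re-implantation.** Section 10.1 gives this one form of re-treatment a firm rule: "A separate sensitivity analysis will be conducted in which the subjects that received a replacement implant are considered non-responders".

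**Early exit.** Section 7.8 requires that "the clinical site should, at a minimum, document Adverse Events and Concomitant Medications changes". It does not ask for a NOSE score.

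**Precedent.** Section 2.2 reports of the prior study: "Three subjects have had other nasal surgery procedures and consequently exited the study; two subjects after the 12 month visit". The third exited after the 18-month visit.

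**The concern.** A subject who has a further nasal operation after the implant can reach the 24-month responder rate in one of two ways. If the subject exits, there is no score and, on an observed-case analysis, the subject drops out of the denominator. If the subject stays, the NOSE score reflects both the implant and the later operation, and a good score counts as response to Latera. Compared with counting such subjects as failures, neither route can lower the rate, and both can raise it.

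The late visits are where this matters. The Protocol Summary says the implant absorbs over about 18 months, and the prior study's operations all came after month 12. A reader will take the 24-month rate as evidence on whether the benefit lasts. As planned, that rate cannot separate lasting benefit from later surgery.

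Data collection is also thin there. Under section 7.1.5 the nasal exam and the health economics questionnaire stop after month 12, and only adverse device effects are collected beyond it. Section 7.5 commits to recording medications. Section 5.3 allows the 18- and 24-month follow-up by telephone or mail. No scheduled item at those visits asks about other nasal surgery or dilator use.

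**Working it through.** **Inputs.** Null proportion 0.50, two-sided 5% exact test, assumed response 66%, 150 subjects with a score, up to 170 enrolled, and 80% response at 6 months in earlier work (all section 10.5). Other nasal surgery in the prior study: 3 of 30, none before the month-12 visit, two after month 12 and one after month 18 (section 2.2).

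**The plan's own figure.** With n = 150 the exact test rejects at 88 or more responders. P(X ≥ 88) for X ~ Bin(150, 0.66) is 97.5%, so the stated power above 90% is correct. Allowing for 10% dropout, 150/0.90 = 167, consistent with up to 170.

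**Share with other surgery.** 3/30 = 10%; exact 95% CI 2.1% to 26.5%. Applied to 170 this is 17 subjects.

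**Exit route, month 24.** Suppose 150 subjects are scored and 17 have left after surgery. The observed-case rate is r/150; with the 17 counted as failures it is r/167.

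| Observed rate | Observed case | Surgery counted as failure | Difference |
|---|---|---|---|
| 66% | 99/150 = 66.0% | 99/167 = 59.3% (exact 95% CI 51.4 to 66.8) | 6.7 points |
| 80% | 120/150 = 80.0% | 120/167 = 71.9% (64.4 to 78.5) | 8.1 points |

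At a true 66% among those scored, the chance that the same exact test rejects at month 24 is 97.5% on 150. With the 17 counted as failures, 97 of 167 are needed, and P(X ≥ 97) for X ~ Bin(150, 0.66) is 67%. Most of that drop comes from estimating a different quantity, and no formal hypothesis is attached to month 24.

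**Stay route, month 24: a ceiling.** If 15 of 150 scored subjects had surgery, all 15 then respond, and 89 of the other 135 respond, the rate is (89 + 15)/150 = 69.3% against 89/150 = 59.3%, a gap of 10 points. If none of the 15 respond, the gap is zero.

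**Month 18.** Share 2/30 = 6.7%. Exit route, share × rate: 6.7% × 66% = 4.4 points and 6.7% × 80% = 5.3 points. The stay-route ceiling is 6.7 points.

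**Months 6 and 12.** The prior study had no such exit before the month-12 visit, so the expected lift is zero. For month 6, 0/30 has an exact two-sided 95% upper limit of 11.6%. With 99 responders the primary test still rejects at 99/171 (p = 0.046) and first fails at 99/172 (p = 0.056), so 22 added failures would be needed to overturn it.

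**Sensitivity to the share.** Over 2.1% to 26.5%, the exit-route lift runs from 0.66 × 2.1% = 1.4 points to 0.80 × 26.5% = 21.2 points, and the stay-route ceiling from 2.1 to 26.5 points. Only 15 of 30 prior subjects completed 18 months, so 3/30 may understate the share. With risk sets of 29 and 15 assumed from the visit counts, it is 1 − (27/29)(14/15) = 13.1%.

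**The case against.** **The observed-case reading is not stated.** Section 10.5 says that all mITT subjects will be used, and the non-responder sentence in section 10.4.2, taken literally, could cover a subject with no score. This stands as an ambiguity. Sizing on subjects with follow-up, and listing missing-as-non-response as a possible sensitivity analysis, both point to observed case. That reading remains an inference.

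**The prior share may not carry over.** Prior subjects had no septal or turbinate treatment (section 2.3.3). Here contributing septal deviation is excluded (section 5.2) and turbinate reduction may be done at the index procedure (section 7.4), so later surgery for those causes may be less likely. The reasons for the prior operations are not given. This stands, and it is why the size is conditional.

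**Other records may identify cases.** Deviations go on an eCRF (section 14.3) and are tabulated (section 10.4.5), and exit reasons are recorded (section 11). Sections 8.1 and 8.3 describe wider event capture than section 7.1.5 does. So a reader who infers that the late data could never be repaired goes too far. What remains is that no dated question is scheduled.

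**Scoring regardless of later surgery is a legitimate estimand.** Agreed. The plan need not replace its main definition, but it should show the other one beside it.

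**The endpoint is secondary.** Section 10.4.9 calls all non-primary endpoints supportive and section 10.2 gives no other formal hypothesis. This limits the consequence without closing the gap.

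**Conclusion.** The point holds for the 18- and 24-month responder rates. The plan fixes a non-responder analysis for re-implantation and has nothing equivalent for other nasal surgery. Neither the per-protocol set nor any listed sensitivity analysis removes a good score obtained after such surgery. If run, missing-as-non-response would catch those who exit, mixed with ordinary loss, while LOCF could carry a pre-surgery response forward.

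The size is about 7 to 8 points at month 24 by exit, and about 4 to 5 points at month 18. It rests on four assumptions: observed-case analysis, the prior share of 3/30 extended to month 24, surgery that reflects inadequate relief, and 24-month response of 66% to 80%, which are month-6 figures.

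Three stronger readings are tempting, and the documents do not support them:
- **That the lift is 10 points.** That is a ceiling which needs every such subject to stay and respond; all three prior subjects exited.
- **That all rates from month 12 on are inflated.** No prior operation preceded the month-12 visit.
- **That the primary result or its power is at risk.** Little effect is expected at month 6, and the stated power is correct.

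This is a worthwhile, low-cost improvement to a supportive endpoint.

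**What to change.** 1. **Sections 10.4.2 and 10.4.3:** add a fixed sensitivity analysis, parallel to the one for re-implants and reported beside the main rate. A subject who had other surgery for nasal obstruction or the nasal valve before a visit is a non-responder at that and later visits, with or without a score. Report the counts. Treat dilator users the same way in a further analysis. The result is still a proportion, so the exact test and Clopper-Pearson interval apply unchanged.
2. **Forms:** add dated yes/no items on other nasal surgery and dilator use at 18 and 24 months, and ask for a NOSE score at early exit.
3. **Missing data:** make missing-as-non-responder a fixed sensitivity analysis at 12, 18 and 24 months.
4. **Reconcile first:** section 7.6 sets a 24-month heading over a nasal valve item worded for 12 months, and section 7.1.5 limits late event capture more narrowly than sections 8.1 and 8.3. Both must be settled before the rule refers to them.

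The cost is a few sentences, two form items and one questionnaire at exit. Someone without sight of the NOSE scores must decide which surgery counts, since too broad a rule would score unrelated operations as failures. The late rate in the added analysis may be lower than the main one.

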10.4.3. ANALYSIS OF THE SECONDARY ENDPOINT(S)

Response proportion as defined in section 10.4.2 will be evaluated for the 1, 3, 12, 18 and 24 month follow-up visits using the same technique as described for the primary endpoint.

Change in nasal airway obstruction from baseline at 1, 3, 6, 12, 18 and 24 months post-procedure as reported by subjects on a VAS 0-100 mm scale (0= no difficulty breathing through nose; 100mm=not-able to breathe through nose) will be analyzed using a mixed model for repeated measures (MMRM). Least-square mean change from baseline and corresponding 95% confidence intervals will be reported.

Baseline VAS score will be analyzed in a separate model, including decongestant use as a covariate. Decongestant use will be considered at baseline only to visualize the turbinate contribution to overall obstruction, thus no decongestant VAS will be assessed at the follow-up visits.

Results from the subject satisfaction questionnaire will be tabulated at 6 months. Sensitivity analyses for missing data will be described in the SAP.

10.4.4. SAFETY ANALYSES

Two analysis sets will be used to summarize adverse events. The ITT analysis set will be used to summarize acute adverse events (through 1 month post procedure), and the mITT analysis set will be used to summarize adverse events over the entire duration of follow-up. The primary safety reporting time-point is 6 months post-implant.

The overall incidence (i.e., number and percent of subjects with 1 or more adverse event) of adverse events, serious adverse device events, serious adverse events, fatal adverse events, and device related events (e.g., possibly, probably or definitely related) will be calculated for the acute phase, through 6 months post-procedure and for the entire duration of follow-up. The overall incidence of mild, moderate and severe events will be calculated by considering the most severe event for each subject.

In addition, the overall incidence for each adverse event type will be calculated. The adverse event types will be classified as defined in section 8.1.1

The implant retrieval rate will be calculated based on the number of implants retrievals per the total number of implants placed.

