4.2. STUDY ENDPOINTS

4.2.1. PRIMARY ENDPOINTS

Primary Efficacy Endpoint: Proportion of treatment responders at 6 months post procedure.

- A responder is defined as a subject that has at least 1 NOSE class improvement or at least 20% NOSE score reduction.

Primary Safety Endpoint: Nasal procedure and Latera device-related adverse events through 6 months.

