8. ASSESSMENT OF SAFETY

8.1. SPECIFICATION OF SAFETY PARAMETERS

All Serious Adverse Events (SAE), Adverse Device Effect (ADE) and Serious Adverse Device Effects (SADE) will be collected and documented through the end of subject participation in the study. In addition, all non-serious device and procedure-related Adverse Events (AE) and all non-serious head and neck, and/or respiratory related AEs will also be collected and documented.

The primary safety endpoint evaluation will consider nasal procedure related and Latera related adverse events through 6 months post-procedure.

The following information for each AE, ADE, SAE and SADE will be collected:

- Date of onset
- Status and/or Outcome
- Date of resolution
- Adverse Event/Effect type (See Section 8.1.1)

In the event of Implant loss or removal, the following information will be documented:

- Implant exposed intranasal at pierce point or exposed on the external skin surface
- Implant retrieved by surgeon or subject
- Whether Implant loss or removal was complete or partial
- SAE or SADE (See Section 8.1.2 and 8.1.3)
- Severity of event (See Section 8.2.1)
- Relation to Study Device and/or procedure (See Section 8.2.2)
- Action taken
- Descriptive narration of Event/Effect

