10.3. ANALYSES DATASETS

Four analysis populations will be considered: The analysis datasets described in the following section apply to the subjects enrolled in the main study (excluding training cases). The training subjects will not be included in the formal analyses for this protocol.

- Intention-to-Treat (ITT) Population: all enrolled subjects who began a nasal Implant procedure, regardless of concomitant turbinate treatment (i.e., Latera alone or in conjunction with turbinate treatment) or re-implant according to this protocol.
- Modified Intention-to-Treat (mITT) Population: all subjects enrolled who received at least one nasal Implant, regardless of concomitant turbinate treatment. Subjects that received a replacement implant will be included in this analysis dataset.
- Per-Protocol (PP) 6 Month Evaluable Population: subjects with 6 month post-Implant NOSE score assessments in clinic or by telephone, regardless of concomitant turbinate treatment. Subjects that received a replacement implant will not be included in this analysis dataset.
- Latera Stand-Alone Population: subjects who receive at least 1 Latera implant without concomitant turbinate treatment.

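### On its natural reading, section 10.4.4 puts the 6-month primary safety summary on mITT, which leaves out subjects whose implant procedure was begun but who received no implant

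*Combined protocol and SAP*

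**What the plan says.** Section 10.3 separates two populations by what happened in the procedure room. ITT is "all enrolled subjects who began a nasal Implant procedure". mITT is "all subjects enrolled who received at least one nasal Implant, regardless of concomitant turbinate treatment". Both exclude training cases.

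Section 10.4.4 gives each a role in safety reporting. For the acute period it says "The ITT analysis set will be used to summarize acute adverse events (through 1 month post procedure". For the rest it says "the mITT analysis set will be used to summarize adverse events over the entire duration of follow-up. The primary safety reporting time-point is 6 months", counted from implantation. The paragraph that follows lists three windows for the incidence tables (acute, through 6 months, whole follow-up) and names no set for any of them.

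Section 4.2.1 defines the primary safety endpoint as "Nasal procedure and Latera device-related adverse events through 6 months". Section 8.1 repeats that both kinds of event count: "The primary safety endpoint evaluation will consider nasal procedure related and Latera related adverse events through 6 months post-procedure".

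**The concern.** The primary safety endpoint covers complications of the procedure as well as effects of an implant left in place. Some of those complications need no retained implant. Sections 2.3.2 and 8.1.1 list hematoma and unintended skin perforation, and section 8.2.2 treats implant delivery as part of device-relatedness. If such an event led the investigator to stop with no implant in place, the subject would belong to ITT but not to mITT.

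Membership of mITT is therefore decided by the outcome of the attempt, and a complication can influence that outcome. Applied to the 6-month summary, the set conditions the primary safety rate on successful placement. For a study of an in-office procedure, attempts that fail are part of the safety question. There is also a problem of coherence: the 1-month and 6-month tables would rest on different subjects, so an incidence meant to accumulate could go down between them.

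**Working it through.** The plan states no figure on this point, so there is none to reproduce. The check sets the definitions side by side and then sizes the effect under stated assumptions.

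**Which subjects differ.** ITT minus mITT is exactly the subjects with a begun procedure and no implant placed. A bilateral case with one side placed stays in mITT.

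**Which set applies at 6 months.** Section 10.4.4 names only two safety sets. ITT is tied to the period through 1 month. mITT is tied to the whole of follow-up, and the 6-month primary time-point comes in the next sentence. No other section provides a 6-month ITT safety table or carries the excluded subjects' events forward.

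**Size.** Inputs:
- Main-study enrolment N = 170 (section 10.5, upper limit), taken as the ITT count.
- k = abandoned procedures with no implant. The documents give no figure; assumed range 0 to 8.
- p = 6-month event rate in implanted subjects. Assumed about 10%, with 5% and 15% as alternatives.
- q = event rate in abandoned cases. Assumed anywhere from 0 to 1.

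The mITT rate is p. The ITT rate is [p(N − k) + qk]/N. The difference, ITT minus mITT, is (k/N)(q − p).

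For one abandoned case with an event (k = 1, q = 1) the difference is (1 − p)/170:
- p = 5%: 0.95/170 = 0.56 points
- p = 10%: 0.90/170 = 0.53 points
- p = 15%: 0.85/170 = 0.50 points

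With whole subjects and p of about 10%:

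| k | mITT | ITT, every abandoned case has an event | Difference | ITT, no abandoned case has an event | Difference |
|---|---|---|---|---|---|
| 0 | 17/170 = 10.0% | 17/170 = 10.0% | 0 | 17/170 = 10.0% | 0 |
| 1 | 17/169 = 10.1% | 18/170 = 10.6% | +0.5 | 17/170 = 10.0% | −0.1 |
| 3 | 17/167 = 10.2% | 20/170 = 11.8% | +1.6 | 17/170 = 10.0% | −0.2 |
| 5 | 16/165 = 9.7% | 21/170 = 12.4% | +2.7 | 16/170 = 9.4% | −0.3 |
| 8 | 16/162 = 9.9% | 24/170 = 14.1% | +4.2 | 16/170 = 9.4% | −0.5 |

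The sign depends on whether q exceeds p.

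**Coherence across windows.** Take k = 3, each with an early event, and suppose 15 of the 167 implanted subjects have an event by 1 month and 17 by 6 months. The 1-month ITT incidence is (15 + 3)/170 = 10.6%. The 6-month mITT incidence is 17/167 = 10.2%. The cumulative rate has fallen although two more subjects have had an event.

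**The case against.** Several points on the other side stand.

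- **The 6-month set is inferred.** Section 10.4.4 does not assign it in so many words, and section 10.1 defers further detail to a SAP to be finalized before database lock. mITT is still the only set left once ITT stops at 1 month. If the sponsor meant something else, the primary safety endpoint has no clearly stated population, and the same edit is needed.
- **The events are not lost.** A reader might infer that complications of stopped procedures vanish from the safety report. They do not: the acute ITT table is prespecified, and most such events would occur early enough to appear in it. What they miss is the summary designated as primary.
- **The direction is not guaranteed.** A procedure can be stopped without any adverse event, and the last two columns of the table show mITT then slightly overstating the rate. A higher event rate in abandoned cases is plausible, but the documents do not show it.
- **Abandonment may be rare or absent.** The prior study in section 2.2 placed 56 implants in 30 subjects, and no abandoned procedure is reported. Investigators must have commercial experience (section 2.3.2) and satisfactory training cases (section 5.4).
- **No test depends on it.** Section 10.2 states no formal safety hypothesis, so this is a descriptive rate.
- **mITT suits late device effects.** Subjects with no implant dilute those rates. That supports keeping mITT after 6 months, but not for an endpoint that includes procedure events.

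**Conclusion.** The concern holds in a limited form. Read naturally, the plan reports its primary safety endpoint in a set that leaves out begun-but-unimplanted subjects, although their procedure and delivery events meet the endpoint definition. The primary rate is understated if those subjects have a higher event rate than implanted subjects, and the 6-month cumulative incidence can then fall below the 1-month figure.

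The size is unknown. It is zero if no procedure is abandoned. Otherwise it is about 0.5 percentage points for each abandoned case with an event, given 170 subjects and an event rate of 5% to 15% among implanted subjects.

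A reader might go further and use the prior study's 4 of 30 subjects with device-related events as the 6-month rate, assume that a few percent of procedures are abandoned, and conclude that the rate is biased downward by a definite amount. The documents do not support that. The 4 of 30 counts device-related events only, in a study followed to 18 months with no event timing given, and 14 of its 30 cases were done in an operating suite under general anesthesia. No abandonment rate is given anywhere, so any range must start at zero.

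**What to change.** In section 10.4.4, name the analysis set for each of the three windows:

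- **Acute, through 1 month:** ITT, as now.
- **Through 6 months (primary safety endpoint):** ITT, with mITT as a supportive table.
- **After 6 months:** mITT may stay for device effects.
- **Implant retrieval:** unchanged, per implant placed.

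The cost is a wording change in the protocol and SAP. The protocol part needs IRB review under section 13.2. No new data item is needed for events up to study exit, because sections 5.5 and 7.8 already require adverse events to be documented at early termination. The primary rate may come out slightly less favourable, and any unimplanted subjects without events add a little event-free denominator. If no procedure is abandoned, the two sets coincide and the change has no effect on the results.
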